# 6.4. Dose Modification

# 6.4.1. Participant-Level Dose Modifications due to Adverse Events

GSK3745417 dose reduction or alternative dosing schedules at a participant or cohort level may be considered based on emerging data.

## Holding daily dosing

Daily dosing will be continued unless there is evidence of ongoing TLS or immune activation in line with the criteria below.

Daily dosing held if:

- Ongoing Grade 3 TLS (see Appendix 11 for Cairo Bishop grading) or Grade 3 electrolyte abnormalities that are not responding to treatment
- Failure of any CRS, fevers, or chills to resolve to Grade ≤1 (with supportive treatment) within 24 hours
- Any new neurological adverse events (except for Grade ≤2 headache which responds to analgesia), until assessment and cause of neurological event is identified
- Investigator judgement that dosing should be held based on the clinical status of patient

### Dose reduction for CRS

In the event of Grade 2 CRS, further dosing can be given with prophylaxis against CRS with steroids, paracetamol/acetaminophen, and antihistamines (as agreed between investigator and MM). Patients with more than one episode of Grade 2 CRS within the same cycle despite prophylaxis should be dose reduced to the next dose level down once dosing resumes. Participants will come off study if more than 2 dose reductions required, or if they require dose reduction below the lowest study dose of 12.5 µg.

In participants who develop CRS requiring holding of daily dosing, Investigators should perform additional LFT and clinical chemistry tests during the dose hold as clinically indicated, and perform the additional investigations outlined in Section 6.4.1.4.

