# **Overall Design and Brief Summary:**

This is a Phase 1, open label, dose escalation study to evaluate safety, pharmacokinetics, and pharmacodynamics of intravenous GSK3745417 in participants with relapsed or refractory AML or high risk MDS.

The study will be conducted in a staged approach consisting of 2 parts. Part 1 will evaluate a dosing schedule of a 5 days on/2 days off schedule for 2 weeks, and then have an additional 2 weeks off dose for observation for a total of 28 days in each cycle (5/2)/5q28d). Once a maximum tolerated dose (MTD) has been established, additional cohorts may be opened to refine dosing frequency optimization. Each cohort will include at least 3 participants and dosing of participants entering the study will be staggered by at least 5 days from D1 of previous patient for the first cohort only. Part 1 will include intra-patient dose escalation for 3 cycles, according to safety and tolerability parameters. The starting dose for Cycle 1 will be escalated in the next dose-escalation cohort until a cohort level starting dose-based MTD is reached. Individual patients may titrate above the starting dose-based MTD based on tolerability. Dose escalation cohorts will start with Cycle 1 at 12.5 µg GSK3745417. Within a cohort for an individual subject the dose may double for Cycle 2, and double again for Cycle 3 based on individual tolerability. The starting dose of subsequent cohorts will increase by 2-fold from Cycle 1 of the previous cohort. Patients may be dose reduced for subsequent cycles if there is lack of tolerability in the previous cycle (Section 6.4). The DLT period will be 28 days starting at Day 1 of Cycle 1 of each cohort. After 3 induction cycles, if a complete response (CR) or partial

response (PR) (IWG) is observed (See Appendix 9) each patient will continue with maintenance weekly dosing at the Cycle 3 dose level until disease progression or unacceptable toxicity. Participants with progressive disease after 3 induction cycles will be withdrawn from study. Participants with stable disease or PR after 3 cycles might receive additional cycles if the assessment by the investigator determined a benefit and GSK Medical Monitor agrees.

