# CONFIDENTIAL

DE Cohort	Screeningª	Cycle (Induction Period)			Follov (post-fin adminis	w-Up al dose stered)	
Study Procedure		Intervent (In-P	tion Period atient)	Observation Period (Outpatient)	TDV⁵	Follow- Up	Notes
Week	≤4	1	- 2	3 - 4	+4		
Day	≤28	-1	1 - 13	14 - 28	+30d		
Urinalysis⁰	x		Х		Х		Sample collection times: Days 1, 8 and 13 of each cycle. If urinalysis is abnormal, a microscopy should be performed.
Coagulation	x		х				Sample collection times: at screening and prior to administration of first dose of GSK3745417 and at Day 8 of each cycle. Additional coagulation samples should be collected in the event of CRS (see Section 6.4.1.4)
Study Intervention	•						· · ·
Administer GSK3745417			X				GSK3745417 will be administered the same dose within each cycle on Days 1 – 5 and Days 8 - 12 QD. Participants will receive up to 3 cycles of treatment before moving to Q1W or Q3W dosing (Section 6.1). See Section 4.1 for maximum duration of study intervention. See Section 4.1 for safety and tolerability parameters to be reviewed prior to each daily dose
Non-Azole Antifungal		х	Х	Х			Non-azole antifungals should be administered if indicated, per local standard, on Day -1 through Day 28 of each cycle.
Tumor Lysis Syndrome Prophylaxis		x					All participants should receive tumor lysis syndrome (TLS) prophylaxis prior to date of first dose of each cycle on Day -1 according to institutional guidelines (e.g., participants should receive IV fluids ± allopurinol and consider alkalization of urine and

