### Table 7Dose-Limiting Toxicities

Participants who withdraw from the study before completing DLT period for reasons other than DLT may be replaced. If a participant experiences a DLT during the DLT period of treatment, the participant will be discontinued from study treatment unless the investigator considers it in the best interest of the participant to continue on study (e.g., in case of symptomatic disease improvement, and/or if the DLT is viewed as preventable in subsequent doses/visits, etc.) and the sponsor approves of the decision.

Guidance for the management of toxicity, including dose modification algorithms, is provided in Section 6.4.

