### 3. ANALYSIS SETS

Analysis Set	Definition / Criteria	Analyses Evaluated
Screened	All participants who were screened for eligibility.	Study     Population
Enrolled	All participants who entered the study (who received GSK3745417 or underwent a post-screening procedure). Note: Screening failures (who never passed screening even if rescreened) and participants screened but never enrolled into the study (met eligibility but not needed) are excluded as they did not enter the study.	Study     Population
Safety	All participants who take at least 1 dose of study intervention. Participants will be analysed according to the intervention they actually received.	

Study Population

Safety

Efficacy

DLT-evaluable	
 
All participants who take at least 1 dose of study intervention and are followed for the DLT observation period or are withdrawn within the DLT observation period due to meeting the DLT criteria.
 
Participants unable to receive at least 70% of scheduled doses within the DLT period for other reasons other than toxicity will not be considered evaluable
 
	Safety
PK	All participants from the Safety Analysis Set for whom a PK sample is obtained and analysed.	• PK

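### The CRS dose-reduction rule conflicts with the same-dose-per-cycle rule, and a participant reduced within Cycle 1 counts by default as a non-DLT at the full cohort dose

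*Protocol*

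**What the plan says.** Four rules meet here.

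- **Reduction for CRS (Protocol 6.4.1).** "Patients with more than one episode of Grade 2 CRS within the same cycle despite prophylaxis should be dose reduced". The size and timing of that reduction are given only as "to the next dose level down once dosing resumes". A participant comes off study after more than two reductions, "or if they require dose reduction below the lowest study dose", which is 12.5 µg.
- **Dose within a cycle (Protocol Table 1, row for administration).** In Part 1 the drug "will be administered the same dose within each cycle". The Synopsis, repeated in Section 4.1, adds: "Patients may be dose reduced for subsequent cycles if there is lack of tolerability in the previous cycle", and refers the reader to Section 6.4.
- **DLT and evaluability (Protocol 4.1.1, SAP 3).** Table 7 names only Grade 3 or 4 CRS as a DLT, but lets the investigator and Medical Monitor jointly call any other event a DLT. The SAP excludes from the DLT-evaluable set "Participants unable to receive at least 70% of scheduled doses within the DLT period" where the reason is not toxicity. Neither document attaches a dose level to those doses.
- **Replacement (Protocol 4.1.1).** "Participants who withdraw from the study before completing DLT period for reasons other than DLT may be replaced".

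SAP 4.2.2 counts DLTs per cohort but assigns adverse events to the dose level at first occurrence.

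**The concern.** The N-CRM relates DLT to dose, so each participant's outcome should belong to the dose entered for that participant. Someone halved part-way through Cycle 1 was not observed for the full window at the cohort dose. Entering that person as 0 DLT at that dose credits tolerance that was not seen.

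The protocol itself treats this event as a tolerability signal: more than one Grade 2 CRS episode in the previous cycle bars intra-patient escalation (4.1.2 and 6.4.1.1). CRS is the first product risk in Table 5, and cohorts may be as small as three. At stake are the escalation steps taken and, in the report, whether a row showing no DLTs in three participants can be read as tolerance of that dose.

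**Working it through.** **1. Do the passages conflict?** The CRS rule directly follows the text on holding daily dosing, and its next paragraph concerns holds of daily dosing. Resuming therefore most naturally means resuming after a hold, in the same cycle. That contradicts Table 1 and does not fit Section 4.1. A next-cycle reading is possible and would remove the conflict, but the rule names no cycle.

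**2. Does the 70% rule catch the case?** Dose levels double, so one level down is half. If the dose is halved after dose k of 10 and all doses are given, the share of the planned cumulative dose is (k + 0.5 × (10 − k))/10:

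- k = 2: 60%
- k = 3: 65%
- k = 5: 75%

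The number of doses given is 10/10 each time, so the participant stays evaluable. The exclusion is in any case confined to shortfalls unrelated to toxicity.

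**3. Effect on the N-CRM.** Inputs from Protocol 9.2 and 4.1: logit(p) = α + β ln(dose/50 µg); α mean −1.7907 (SD 1.6787); ln β mean 0.1961 (SD 0.1706); correlation −0.7729; limit P(p ≥ 33%) < 25%. The average sample sizes in Table 14 (14, 20, 22) cannot be reproduced, because the true DLT rates are in Figure 7, which is not available in the text. As a check value, the prior P(p ≥ 33%) at 12.5, 25, 50, 100 and 200 µg is 7.1%, 14.0%, 26.0%, 44.1% and 66.4%.

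Assume earlier cohorts had 0/3 DLTs and one of three in the current cohort is reduced. Posterior P(p ≥ 33%) at the next dose, by grid integration (figures can move by 0.1 point with the grid):

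| Cohort → next dose | Non-DLT at cohort dose (0/3) | Credited one level lower | Left out (0/2) | Called a DLT (1/3) |
|---|---|---|---|---|
| 25 → 50 µg | 6.6% | 7.4% | 8.5% | 35.7% |
| 50 → 100 µg | 11.6% | 12.9% | 14.4% | 43.1% |
| 100 → 200 µg | 22.6% | 24.7% | 26.8% | 56.9% |

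Leaving the participant out adds 1.9, 2.8 and 4.2 points. Of these steps only the last crosses 25%, and crediting the lower dose there stays just inside the limit.

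**4. The 12.5 µg cohort.** No lower level exists, so the participant comes off study. Without a DLT call, and if not followed for the full window, that person is outside the DLT-evaluable set and may be replaced. Going from 0/3 to 0/2 raises P(p ≥ 33%) at 25 µg from 4.9% to 6.7%; a replacement without a DLT returns it to 4.9%. The event then does not show in the DLT count.

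**5. Frequency.** The documents give none. Let q be the share reduced in Cycle 1 and r their DLT risk had they stayed at full dose. The understatement of the full-dose DLT rate is at most q × r. For assumed q of 5% to 30% and r of 16% to 50%, this runs from 0.05 × 0.16 = 0.8 points to 0.30 × 0.50 = 15 points. The chance of at least one such participant in a cohort of three is 1 − (1 − q)³: 14% at q = 5%, 27% at 10%, 66% at 30%.

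**The case against.** The strongest reply is that the plan already has safeguards. The discretionary clause in Table 7 allows a DLT call. Section 4.1.2 requires non-DLT toxicities to be reviewed before each decision, and Section 4.1 lets the team lower the recommended dose at any time. Grade 2 CRS is not an automatic DLT by design, so not counting it is not in itself an error. Reporting is partly covered too: Protocol 9.4.2.2 plans a summary of AEs leading to dose reduction, SAP 4.5.1 lists scheduled and actual doses, and SAP 4.3.2 counts CRS participants and occurrences.

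This limits the consequence but does not close the gap. None of these provisions says whether a participant reduced in Cycle 1 is evaluable, or at which dose that participant enters the model.

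A reader might go further and infer that the protocol forces a within-cycle reduction, that the bias always runs towards lower apparent toxicity, or that one participant decides escalation. The documents do not support these. The next-cycle reading remains open. Leaving out a non-DLT raises the modelled toxicity, as the 12.5 µg case shows. The crossing at 200 µg needs the participant to be left out without replacement, and 56.9% needs a DLT call that Table 7 leaves to judgment.

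**Conclusion.** The concern stands as a should-fix. The passages on changing the dose within a cycle conflict on their most natural reading. By default, and absent a discretionary DLT call, a Cycle 1 reduction is credited as full-dose tolerance in the N-CRM and in the per-cohort DLT summary.

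For one affected participant in three, choosing to leave that person out rather than count a full-dose non-DLT is worth about 2 to 4 points of overdose probability. It changes the decision only at the step to 200 µg. These figures assume clean earlier cohorts of three and the stated prior. The overall bias cannot be sized without the frequency of recurrent Grade 2 CRS despite prophylaxis. SAP 4.7 and 4.8 state that Part 1 recruitment has finished and that no interim analysis will be run, and the SAP specifies no N-CRM analysis, so the live consequence is how the DLT summary is read.

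**What to change.** 1. Reconcile Protocol 6.4.1 (reduction for CRS), Table 1, the Synopsis and Section 4.1 on whether the dose may change within a cycle. Which rule applies is a clinical decision for the sponsor and is not proposed here.
2. In Protocol 4.1.1 and SAP 3, count the 70% on doses given at the cohort's assigned Cycle 1 dose. This alone is not enough, because the exclusion covers only shortfalls unrelated to toxicity.
3. So also state how a participant whose Cycle 1 dosing was reduced or stopped for drug-related toxicity short of a DLT enters the N-CRM: not as a full-dose non-DLT, and with a sensitivity run for any escalation decision still to be made.
4. In the per-cohort DLT summary of SAP 4.2.2, add a row: *Cycle 1 dose reduced or stopped for toxicity, no DLT*. It should include anyone in the 12.5 µg cohort who came off study for this reason. After termination this is the part that can still be used.

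The cost is a few lines of wording and one table row. In a running trial, an occasional cohort might need one more evaluable participant.

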## 6.4.1.1. Intra-Patient Dose Escalation

Intra-patient dose escalation is permitted for induction treatment cycles 2 and 3 depending on safety and tolerability of the first dosing cycle. To allow intra patient dose escalation for the next dosing cycle:

- Investigator and MM must both consider that dose escalation is in the best interests of the participant
- Participant must have received at least 7 of the 10 doses in the prior cycle
- Participant must not have experienced:
  - Any Grade  $\geq$ 3 AE
  - $\circ$  Grade  $\geq$ 3 TLS
  - A DLT (which includes Grade 3 CRS, all non-hematologic Grade 3 events with a few exceptions as per Table 7)
  - More than 1 episode of Grade 2 CRS in the previous cycle
  - Evidence of ongoing immune activation during the observation period (sustained or intermittent Grade ≥2 fever ongoing after the first week of the observation period)

## 6.4.1.2. Tumor Lysis Syndrome

Tumor lysis syndrome (TLS) may occur in participants treated with GSK3745417 as it has demonstrated a direct cell killing mechanism in AML cells. Laboratory or Clinical TLS should be diagnosed according to the Cairo Bishop criteria (Cairo, 2004). In the event of TLS, Investigators should use clinical judgement and follow institutional guidelines for prophylaxis and symptom management of TLS.

Participants should be assessed for TLS risk prior to each dose, including evaluation of tumor burden, comorbidities, and renal function, and prior to each dosing with GSK3745417 should be admitted to hospital the day before first dose of each induction cycle or maintenance dose, and receive prophylaxis for TLS in line with institutional guidance. Blood clinical chemistry must be monitored every 6 hours for the first 48 hours of the first dosing cycle, and each cycle with a dose increase. Participants are hospitalized throughout the 2-week dosing period of each induction treatment cycle and TLS prophylaxis should continue alongside daily dosing of GSK3745417 as clinically indicated.

Assessment	Result Range
Uric acid	≥476 µmol/L (≥8.0 mg/dL) or 25% increase from baseline
Potassium	≥6.0 mmol/L or 25% increase from baseline
Phosphorus	≥1.45 mmol/L (≥4.5 mg/dL; adults) or 25% increase from baseline
Calcium	≤1.75 mmol/L (≤7.0 mg/dL) or 25% decrease from baseline

#### Table 8 Cairo Bishop Definition of Laboratory TLS

#### Table 9 Cairo Bishop Definition of Clinical TLS

Creatinine: x ≥1.5 ULN
Cardiac arrythmia/sudden death
Seizure

For grading of TLS, refer to Cairo Bishop grading in Appendix 11.

## 6.4.1.3. Infusion Reaction

Infusion reactions typically develop within 30 minutes to two hours after initiation of drug infusion, although symptoms may be delayed for up to 48 hours. There are multiple mechanisms known to lead to infusion-related reactions including both IgE-dependant anaphylactic and non-IgE dependent anaphylactoid hypersensitivities. Infusion reactions may affect any organ system in the body. Most are mild in severity, although severe and fatal reactions can occur. As a group, infusion reactions (including both cytokine-mediated and allergic) usually occur during or within a few hours of drug infusion. Occasionally, a reaction may occur one to two days after administration. The NCI-CTCAE (version 5.0) [NCI, 2017] for grading adverse reactions during the infusion of a pharmacological or biological substance has a term for grading the severity of infusion reactions and separate terms for grading allergic reactions, anaphylaxis, and cytokine release syndrome. The use of these separate terms in grading severity of the event may be useful for classifying the nature of an infusion reaction for research purposes; they are less useful for clinical care, since it may not be obvious if the participant is having an allergic infusion reaction or a non-allergic infusion reaction.

Clinically, infusion reactions may present with fever, chills, flushing, itching, urticaria, and/or angioedema, repetitive cough, sudden nasal congestion, shortness of breath, chest tightness, wheeze, sensation of throat closure or choking, and/or change in voice quality, faintness, tachycardia (or less often bradycardia), hypotension, hypertension and/or loss of consciousness, nausea, vomiting, abdominal cramping, and/or diarrhea, sense of impending doom, tunnel vision, dizziness, and/or seizure, severe back, chest, and pelvic pain.

#### 6.4.1.4. Cytokine Release Syndrome

Cytokine release syndrome, and severe, cytokine "storm", has been identified as a sequelae of immune system activation associated with infusion reactions.

Prophylaxis for CRS is not mandated. However, if a participant experiences CRS, prophylaxis with antihistamines and paracetamol is permitted on subsequent infusions. Steroids may also be considered after discussion with the Medical Monitor.

Table 11 provides the recommended management of CRS according to grade, which has been further adapted from CTCAE for use with immunotherapy and should be implemented in accordance with institutional guidelines. Symptoms can mimic those seen with infection. The diagnosis of CRS is clinical and is supported by the exclusion of infection as well as the presence of increased cytokine levels and other biomarkers. Assessment and treatment guidelines are provided below in alignment with (the Society for Immunotherapy of Cancer SITC) guidelines (Maus, 2020). In the event of CRS, Investigators may also follow institutional guidelines for symptom management; additional guidance can be found in the published literature (Lee, 2019).

If CRS is suspected, in addition to assessment for infection, the following tests should be conducted **every day for the first week** and approximately **every other day thereafter** until symptoms are improving or an alternative diagnosis is confirmed:

- Local tests:
  - Clinical chemistry including LFTs, hematology, ferritin and coagulation, as well as C-reactive protein (CRP) labs;
  - Troponin, and *N*-terminal pro B-type natriuretic peptide (NT-proBNP) / BNP tests;
- Central tests: See Table 10 for central or local biomarker testing

CCI

 $\circ$  cytokine-profiling as described in Section 8.6.

Grade	Clinical Presentation for Grading Assessment 	Management Guidelines
1	Temperature ≥38.0 °C	Vigilant supportive care  Assess for infection and treat 
2	Temperature ≥38.0 °C with hypotension not requiring vasopressors and/or hypoxia requiring the use of oxygen delivered by low-flow nasal cannula (≤6 L/minute) or blow-by.	Monitor cardiac and other organ function Vigilant supportive care  Assess for infection and treat  Treat hypotension with fluid Administer $O_2$ for hypoxia  Consider administering tocilizumab $\pm$ corticosteroids 
3	Temperature ≥38.0 °C with hypotension requiring a vasopressor with or without vasopressin and/or hypoxia requiring high- flow nasal cannula (>6 L/minute), facemask, non-rebreather mask, or venturi mask not attributable to any other cause 	Monitor participant very closely for cardiac and other organ dysfunction. Most likely will require monitoring in an intensive care unit (ICU). Vigilant supportive care  Assess for infection and treat  Treat hypotension with fluid and pressors  . Administer O 2 for hypoxia. Administer tocilizumab ± corticosteroids 
4	Temperature ≥38.0 °C with hypotension requiring multiple vasopressors (excluding vasopressin) and/or hypoxia requiring positive pressure (eg: CPAP, BiPAP, intubation and mechanical ventilation)	Manage participant in ICU Intensive supportive care including mechanical ventilation, fluids, pressors, antibiotics and other measures as required  Administer tocilizumab ± corticosteroids 
5	Death	

### Table 11 Management Guidelines for Cytokine Release Syndrome

Fever is defined as temperature ≥38°C not attributable to any other cause. In patients who have CRS then
receive antipyretic or anti-cytokine therapy such as tocilizumab or steroids, fever is no longer required to grade
subsequent CRS severity. In this case, CRS grading is driven by hypotension and/or hypoxia.

- CRS grade is determined by the more severe event: hypotension or hypoxia not attributable to any other cause. For example, a patient with temperature of 39.5°C, hypotension requiring 1 vasopressor, and hypoxia requiring low-flow nasal cannula is classified as grade 3 CRS.
- Low-flow nasal cannula is defined as oxygen delivered at ≤6 L/minute. Low flow also includes blow-by oxygen delivery, sometimes used in pediatrics. High-flow nasal cannula is defined as oxygen delivered at >6 L/minute.
- 4. Supportive care includes monitor fluid balance, maintain adequate hydration and blood pressure
- Assessment and treatment to include history and physical, blood and urine cultures, imaging studies, administration of antimicrobial agents for concurrent bacterial infections, and for treatment of fever and neutropenia as per institutional practice; and antipyretics, analgesics as needed.
- Given that prolonged fluid resuscitation without pressor use is associated with worse outcome and because early and aggressive supportive care, early use of vasopressors, and timely anti-cytokine therapy are paramount to mitigating life-threatening CRS.
- 7. Other immunosuppressor agents may be used, including TNF $\alpha$  and IL-1R inhibitors. Source: (Lee, 2019)

